9.2 SAFETY ENDPOINTS

- Safety parameters (adverse events [including adjudicated cardiovascular events], laboratory data, and vital signs) assessed throughout the study.

Observation period

The observation of safety data will be as follows:

- **PRE-TREATMENT period:** The pre-treatment observation period is defined from the signed informed consent up to the first dose of double-blind IMP injection.
- **DOUBLE-BLIND TEAE period:** The double-blind TEAE observation period is defined as the time from the first dose of double-blind IMP to the last dose of double-blind IMP administration + 70 days (10 weeks) or the first administration in the OLTP, whichever comes first.
- **OPEN-LABEL TEAE period:** The open-label TEAE observation period is defined as the time from the first dose of open-label IMP injection to the last dose of open-label IMP injection + 70 days (10 weeks).
- **POST-TREATMENT period:** The Post-treatment observation period is defined as the time starting the day after the end of the TEAE period up to the end of the study (see definition in [Section 6.2](#)).

Note: Double-blind and open-label TEAE periods will be defined for the long-term safety at the time of the first analysis.

- **TEAE observation period for long-term safety of alirocumab (DBTP and OLTP):**

- For 150 mg Q4W group and 150 mg Q2W group: The time from the first dose of double-blind IMP injection to the last dose of IMP injection (double-blind or open-label) + 70 days (10 weeks).
- For placebo group: The time from the first dose of open-label IMP injection to the last dose of open-label IMP injection + 70 days (10 weeks).

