10.1.4 Open-label treatment period (Study Site Visits or Phone Call Visits)

10.1.4.1 Visit 10 / Week 12 (Day 85 ± 3): End of DBTP and Start of OLTP

Note: The OLPT starts from this visit and it is also the last visit of the DBTP. Blood sample should be collected before the IMP administration. The patient who performs self-IMP administration during the DBTP will continue the self-IMP administration at his/her home during the OLTP. Site staff has to carefully monitor the IMP administration compliance and AEs and SAEs collection through phone-visit call.

- On-site visit.
- Perform physical examination.
- Measure body weight.
- IVRS / IWRS contact for allocation of a treatment kit and the IMP will be supplied before Week 24 scheduled visit.

Note: All patients will be treated with alirocumab 150 mg Q4W from this time point.

- IMP administration and compliance check, and 30 minutes observation after the IMP administration.
- Review patient's diet. Patient should be on a diet recommended by the Japan Atherosclerosis Society Guideline or equivalent.
- Record concomitant medication.
- Measure vital signs including HR and BP.
- Collect AEs / SAEs information.
- Record 12-lead ECG.
- Obtain fasting blood sample for:
 - Lipids: total-C, measured and/or calculated LDL-C, HDL-C, TG, non-HDL-C, Apo-B, Apo A-1, Apo-B / Apo A-1 ratio, and Lp(a).
 - Hematology: CBC including hematocrit, RDW, reticulocyte count, hemoglobin, red blood cell count, white blood cell count with differential count and platelets. (Reticulocyte count and haptoglobin are measured only when hemoglobin is decrease with $\geq 1.5\text{g/dL}$ from the baseline).
 - Chemistry: glucose, sodium, potassium, chloride, bicarbonate, calcium, phosphorous, urea nitrogen, creatinine, eGFR, uric acid, LDH, total protein, albumin, haptoglobin and γ -GT.
 - CPK.
 - Liver panel (ALT, AST, ALP, and total bilirubin).
- Urinalysis (dipstick and microscopy).
- Urine pregnancy test (WOCBP).

- HbA_{1c}
- Anti-alirocumab antibodies.
- Reminders:
 - An appointment will be given for the next study site visit (Week 16).

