2.1.4 Safety endpoints

The safety analysis will be based on the reported adverse events (AEs) and other safety information, such as clinical laboratory data, vital signs, and electrocardiogram (ECG).

Observation period

The observation period starts from the time when the patient gives informed consent and will be divided into following periods:

- The PRE-TREATMENT period is defined from the signed informed consent up to the first dose of double-blind IMP injection.

- The double-blind treatment-emergent adverse event (TEAE) period is defined as the time from the first dose of double-blind IMP injection to the last dose of double-blind IMP injection + 70 days (10 weeks) for patients not entering into the OLTP. For patients entering into the OLTP, the TEAE period will be truncated at the day before the first open-label IMP injection.

The double-blind TEAE period will include:

- The double-blind TREATMENT period: defined as the time from the first double-blind IMP injection up to the day of last double-blind IMP injection (active or placebo depending on the Q2W or Q4W dosing regimen) + 21 days. The treatment period will end approximately 35 days after last active injection for most of the patients randomized in the alirocumab 150 mg Q4W arm since last planned injection at Week 10 is a placebo injection. 35 days is considered appropriate since the effect of alirocumab 150 mg Q4W is expected to be maintained during the 4-week dosing interval.
- The double-blind RESIDUAL TREATMENT period: defined as the time from the day of last dose of double-blind IMP injection +22 days up to the day of last dose of double-blind IMP injection +70 days (10 weeks) for patients not entering into the OLTP. For patients entering into the OLTP, the RESIDUAL TREATMENT period will be truncated at the day before the first open-label IMP injection.
- The double-blind POST-TREATMENT period: defined as the time starting the day after the end of the double-blind TEAE period (i.e., 71 days after the day of last dose of double-blind IMP injection) for patients not entering into the OLTP.
- The open-label TEAE period is defined as the time from the first dose of open-label IMP injection to the last dose of open-label IMP injection + 70 days (10 weeks).

The open-label TEAE period will include:

- The open-label TREATMENT period defined as the time from the first dose of open-label IMP injection up to the day of last dose of open-label IMP injection + 21 days.

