2.1.4.3 Laboratory safety variables

Clinical laboratory data consists of blood analysis, including hematology, clinical chemistry, and urinalysis. Clinical laboratory values after conversion will be analyzed into standard international units. International units will be used in all listings and tables. Clinical laboratory values converted into conventional (US) units will be also available in the database. Analyses can be provided upon request.

Unless otherwise specified below, blood samples for clinical laboratories were to be collected during:

- Screening period at Visit 2 (Week -3)
- DBTP at Visit 4 (Week 0), Visit 10 (Week 12) /or permanent treatment discontinuation
- OLTP at Visit 13 (Week 24), Visit 16 (Week 36), Visit 19 (Week 48), and Visit 23 (Week 64) /or permanent treatment discontinuation

- Follow-up period (Visit 24 [Week 72]) in case of abnormality at Visit 23 (Week 64).

The laboratory parameters (excluding those considered as efficacy parameters) will be classified as follows:

- Hematology:
 - Red blood cells and platelets:
red blood cell count, hemoglobin, red blood cell distribution width (RDW), reticulocyte count, hematocrit, platelets, haptoglobin;
 - White blood cells:
white blood cell count, neutrophils, lymphocytes, monocytes, basophils, eosinophils.
- Clinical chemistry:
 - Metabolism: glucose, total protein, albumin, creatine phosphokinase;
 - Electrolytes: sodium, potassium, chloride, bicarbonate, calcium, phosphorus;
 - Renal function: creatinine, glomerular filtration rate (eGFR), urea nitrogen, blood uric acid;
 - Liver function (also measured during DBTP at Week 4 and Week 8, except gamma glutamyl transferases [GGT] and lactate dehydrogenase [LDH]):
ALT, aspartate aminotransferase (AST), alkaline phosphatase (ALP), GGT, total bilirubin, and in case of total bilirubin values above the normal range, must include direct and indirect bilirubin, LDH.
- Hepatitis screen:
anti-hepatitis-C antibody (at Week -3 and Week 64/or permanent treatment discontinuation).

Technical formulas are described in [Section 2.5.1](#).

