2.4.5 Analyses of safety data

Safety analyses will be conducted using data of the DBTP and OLTP. The summary of safety results will be presented separately for the DBTP on the safety population and OLTP on the OLT population. Besides, safety analyses performed on the alirocumab exposed period (see [Section 2.1.4](#)) will be conducted on the alirocumab safety population to evaluate long-term safety at the first step analysis.

The analyses performed on the DBTP will be presented by treatment group while the analyses performed on the OLTP or the alirocumab exposed period will be presented by overall patients. No formal inferential testing will be performed. Summaries will be descriptive in nature. All summaries of safety results described below will be presented for each observation period respectively, unless otherwise noted.

General common rules

All safety analyses will be performed using the following common rules:

- Safety data in patients who do not belong to the safety population (eg, exposed but not randomized) will be listed separately
- The baseline value for both double-blind and open-label treatment period is defined as the last available value before the first double-blind IMP injection, except otherwise specified.
- The potentially clinically significant abnormality (PCSA) values are defined as abnormal values considered medically important by the Sponsor according to predefined criteria/thresholds based on literature review and defined by the Sponsor for clinical laboratory tests, vital signs, and ECG (PCSA defined in the document “Analysis and reporting safety data from clinical trials through the Clinical Study Report (CSR) (Version Number: 3.0)” [[Appendix A](#)])

Considering that the threshold defined in the PCSA list for monocytes and basophils can be below the ULN, the following PCSA criterion will be used for the PCSA analysis of monocytes and basophils:

- PCSA criterion for monocytes: >0.7 Giga/L or $>$ ULN (if $ULN \geq 0.7$ Giga/L);

- PCSA criterion for basophils: >0.1 Giga/L or $>$ ULN (if $ULN \geq 0.1$ Giga/L).
- PCSA criteria will determine which patients had at least 1 PCSA during the TEAE period, taking into account all evaluations performed during the TEAE period, including unscheduled or repeated evaluations.
- The treatment-emergent PCSA denominator by group for a given parameter will be based on the number of patients assessed for that given parameter at least once during the TEAE period.

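### The SAP ends the double-blind TEAE period the day before the first open-label injection, so TEAE-based double-blind abnormality tables omit the Week 12 safety assessments of patients entering open label

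*SAP*

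**What the plan says.** **The boundary.** SAP 2.1.4 gives patients who do not enter open label a double-blind TEAE period of last double-blind injection plus 70 days. For the others: "For patients entering into the OLTP, the TEAE period will be truncated at the day before the first open-label IMP injection". Protocol 9.2 cuts at a different point: last double-blind dose plus 70 days "or the first administration in the OLTP, whichever comes first". The protocol synopsis agrees with 9.2. SAP 1.5 and 1.6 both record no modification.

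**The sub-periods.** SAP 2.1.4 describes the TEAE period as including a TREATMENT period that runs "up to the day of last double-blind IMP injection (active or placebo depending on the Q2W or Q4W dosing regimen) + 21 days". It writes the open-label truncation into the RESIDUAL sub-period but not into TREATMENT.

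**The Week 12 visit.** Protocol 10.1.4.1 says of this visit: "The OLPT starts from this visit and it is also the last visit of the DBTP". Blood is drawn there before the injection, and open-label alirocumab starts there. SAP 2.1.4.3 lists the general safety laboratory samples as "DBTP at Visit 4 (Week 0), Visit 10 (Week 12) /or permanent treatment discontinuation".

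**The tables.** Under SAP 2.4.5, potentially clinically significant abnormalities (PCSAs) are identified "taking into account all evaluations performed during the TEAE period", and the denominator is the patients assessed at least once in that period. The haemoglobin-decrease, ALT-increase and eDISH displays (2.4.5.3), the abnormal-ECG count (2.4.5.5) and the HbA1c PCSA table (2.4.6) are also tied to the TEAE period.

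**The concern.** Ending a period the day before the next one starts normally does no harm. Here the visit that closes the double-blind phase is also the visit at which open-label dosing starts, so the last double-blind assessments carry the same date as the first open-label injection. For most safety parameters that visit is the only scheduled post-baseline assessment on randomised treatment.

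At stake are the placebo-controlled abnormality tables. The open-label and alirocumab-exposed summaries are presented for all patients together (SAP 2.4.5), so they cannot stand in for a comparison with placebo. CPK abnormalities by history of statin side effects (SAP 2.4.5.3) are among the affected displays and matter particularly in this population.

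**Working it through.** **Inputs**

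- Visit days from the protocol flow chart, Day = 7 × week + 1: Week 8 = Day 57, Week 10 = Day 71, Week 12 = Day 85. The windows at Weeks 10 and 12 are ±3 days.
- Last planned double-blind injection: Week 10. The last active injection in the Q4W arm is Week 8, "since last planned injection at Week 10 is a placebo injection" (SAP 2.1.4).
- First open-label injection: the Week 12 visit (protocol 10.1.4.1).

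**Reproducing the SAP's figure.** TREATMENT end = 71 + 21 = Day 92 (Week 13). Days since the last active Q4W injection = 92 − 57 = 35, which matches the SAP's figure of about 35 days. The SAP therefore intends the TREATMENT period to run past Week 12.

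**The two end points.** TEAE end = 85 − 1 = Day 84. The sub-period outlasts its parent by 92 − 84 = 8 days. Over the visit windows:

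- smallest excess: (68 + 21) − (88 − 1) = 89 − 87 = 2 days
- largest excess: (74 + 21) − (82 − 1) = 95 − 81 = 14 days

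**Where Week 12 falls.** If the assessments and the injection share date d, the TEAE period ends on d − 1, so the assessments are outside it for every d. The earliest TREATMENT end is Day 89 and the latest in-window Week 12 is Day 88, so they are always inside TREATMENT when the Week 10 injection was given. If Week 10 was missed, TREATMENT ends at 57 + 21 = Day 78 and Week 12 is outside that as well.

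**Scheduled post-baseline double-blind assessments inside the TEAE period, patients entering open label**

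| Parameter | Scheduled weeks | SAP boundary | Protocol boundary, pre-dose counted |
|---|---|---|---|
| Haematology | 12 | 0 of 1 | 1 of 1 |
| Chemistry, including GGT and LDH | 12 | 0 of 1 | 1 of 1 |
| CPK | 12 | 0 of 1 | 1 of 1 |
| Urinalysis | 12 | 0 of 1 | 1 of 1 |
| HbA1c | 12 | 0 of 1 | 1 of 1 |
| ECG | 12 | 0 of 1 | 1 of 1 |
| Liver panel (ALT, AST, ALP, bilirubin) | 4, 8, 12 | 2 of 3 | 3 of 3 |

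**Denominators.** For the Week-12-only parameters, what remains is mainly patients who do not enter open label, plus those with unscheduled samples. The documents do not state how many will not enter. As an illustration, assume that the protocol's dropout rate (30% in 12 months, exponential) gives the share not entering: 1 − 0.7^(12/52) = 0.079, and 53 × 0.079 ≈ 4 patients per arm.

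**Which period the samples fall into instead.** The open-label TEAE period starts with the first open-label dose. If clock times are used, pre-dose Week 12 samples fall in neither period. If only dates are used, they fall in the open-label period.

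**The case against.** It can be argued that this is a drafting conflict in a descriptive safety analysis, that the SAP's intent is plain, and that the data are reported elsewhere. Much of that is right, and three stronger readings that a reader might infer are not supported.

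- *That the randomised comparison has no post-baseline laboratory data.* SAP 2.4.5 and 2.4.5.3 also call for by-visit summaries and for last and worst on-treatment values by group. The last and worst values use the TREATMENT period, which covers Week 12. HbA1c has its own by-visit summary (2.4.6). The loss is confined to TEAE-based tables.
- *That all PCSA denominators collapse.* The liver panel keeps Weeks 4 and 8, and heart rate and blood pressure are measured at every visit from Week 2 to Week 10. Unscheduled samples count too.
- *That placebo patients' Week 12 findings will be counted as open-label alirocumab findings.* This happens only under date-only logic, which no section prescribes for these data. The SAP uses date and time for its baseline cut.

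The intent argument also has force. The SAP places Week 12 in the double-blind period for laboratory, ECG and HbA1c data, ends the double-blind on-study period at that visit, and runs antibody data up to the first open-label injection (2.1.6, 2.3.3). But the TEAE rule is explicit. The statement that TREATMENT is included in the TEAE period does not repair it: taken at face value, it would count Days 85 to 92, when former placebo patients are on open-label alirocumab, as double-blind.

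The window tables of SAP 2.5.4 are not in the available text. They could say how Week 12 samples are assigned to a visit, but the PCSA rule refers to the TEAE period, not to visit windows.

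**Conclusion.** The boundary is wrong as written. It departs from protocol 9.2 without being declared, and it is inconsistent with the SAP's own TREATMENT sub-period, which ends 8 days later on schedule (2 to 14 days over the windows).

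For patients entering open label, the TEAE-based double-blind tables would contain no scheduled post-baseline value for the six Week-12-only groups of parameters, and the liver-based ones would lose 1 of 3 panels. Denominators for the Week-12-only parameters would then rest mainly on a small group selected after randomisation. The worst on-treatment values would include Week 12 abnormalities that the PCSA tables omit. The abnormal-ECG count has no other table to fall back on.

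This rests on the planned course: Week 12 assessments and the first open-label injection on the same date, and the Week 10 injection given. Samples drawn on an earlier date would still count. The efficacy analyses do not use this boundary.

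**What to change.** In SAP 2.1.4:

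1. End the double-blind TEAE period at the first open-label injection, as protocol 9.2 does.
2. Assign Week 12 assessments made before that injection to the double-blind period. The protocol states the pre-dose order at Week 12 for blood but not for ECG, so add a rule for missing times; SAP 2.5.3 already has one for Week 0.
3. Start the open-label period after that injection.
4. Cap the double-blind TREATMENT period at the same point, and align the RESIDUAL truncation with it.

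The cost is a few sentences and one derivation rule, with no new data. It should be settled before the first database lock, because the first-step analysis produces these tables.

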8.1.2 Timing of administration

Screening period (from Week -3 to Week 0): Training Injection

During the screening period, a training injection is planned on Week -1 with a placebo for alirocumab. If needed, a second training injection is authorized before the randomization visit. It is noted that further training with the scheduled double-blind / open-label IMP can be done at any time during the study as necessary.

Double-blind treatment period (from Week 0 to Week 12):

During the double-blind treatment period, patients will be randomized to receive:

- Alirocumab 150mg Q4W alternating with placebo for alirocumab Q4W
OR
- Alirocumab 150 mg Q2W
OR
- Placebo for alirocumab Q2W.

Alirocumab will be administered at Week 0, Week2, Week 4, Week 6, Week 8, and Week 10 (Q2W), or at Week 0, Week 4, and Week 8 with alternating placebo for alirocumab administration at Week 2, Week 6, and Week 10 (Q4W). The first IMP administration at Week 0 will start as soon as possible after the call for randomization using the treatment kit number provided by the IWRS. Patients will be monitored at the study site for at least 30 minutes after the first IMP administration.

All IMP injections will be conducted at the study site under direct site staff supervision after all study assessments have been performed and all laboratory samples have been collected.

Open-label treatment period (from Week 12 to Week 64):

All patients will receive alirocumab 150 mg Q4W from the beginning of the OLTP (Week 12). At the beginning of the OLTP, all patients will be monitored at the study site for at least 30 minutes after the first IMP administration.

At Week 24, the up-titration to alirocumab 150 mg Q2W will be conducted through interactive Web Response System (IWRS) under the following circumstances:

- In patients with heFH or in patients with non-FH with documented CHD, LDL-C is ≥ 100 mg/dL (2.59 mmol/L) at Week 20.
- In patients with non-FH classified as primary prevention category III, LDL-C is ≥ 120 mg/dL (3.10 mmol/L) at Week 20.

In patients with alirocumab 150 mg Q4W, the last injection will be conducted at Week 60. In patients with up-titrated alirocumab 150 mg Q2W, the last injection will be conducted at Week 62.

All IMP injections can be conducted home if patients are able to perform (See [Section 10.1.4](#) and [Section 10.1.4.4](#)).

Throughout the entire study duration:

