- The open-label RESIDUAL TREATMENT period: defined as the time from the day of last dose of open-label IMP injection +22 days up to the day of last dose of open-label IMP injection +70 days (10 weeks).
- The open-label POST-TREATMENT period: defined as the time starting the day after the end of the open-label TEAE period (i.e., 71 days after the day of last dose of open-label IMP injection).

Observation periods below will be analyzed at the first step analysis only.

- The alirocumab exposed TEAE period is defined as follows :
 - For alirocumab 150 mg Q4W group and alirocumab 150 mg Q2W group: The time from the first dose of double-blind IMP injection to the last dose of IMP injection (double-blind or open-label) + 70 days (10 weeks).

- For placebo Q2W group: The time from the first dose of open-label IMP injection to the last dose of open-label IMP injection + 70 days (10 weeks).

The alirocumab exposed TEAE period will include:

- The alirocumab exposed TREATMENT period: defined below:
 - For alirocumab 150 mg Q4W group and alirocumab 150 mg Q2W group: The time from the first dose of double-blind IMP injection to the last dose of IMP injection (double-blind or open-label) + 21 days.
 - For placebo Q2W group: The time from the first dose of open-label IMP injection to the last dose of open-label IMP injection + 21 days.
- The alirocumab exposed RESIDUAL TREATMENT period: defined below:
 - For alirocumab 150 mg Q4W group and alirocumab 150 mg Q2W group: The time from the day of last dose of IMP injection(double-blind or open-label) +22 days up to the day of last dose of IMP injection(double-blind or open-label) +70 days (10 weeks).
 - For placebo Q2W group: The time from the day of last dose of open-label IMP injection +22 days up to the day of last dose of open-label IMP injection +70 days (10 weeks).

The double-blind on-study observation period is defined as the time from the day of first dose of double-blind IMP injection until the last protocol planned double-blind visit of the patient. The last protocol planned double-blind visit is defined as the follow-up visit if done, or a maximum of 20 weeks after the randomization of the patient, for patients not proceeding into OLTP. For patients proceeding into OLTP, the last protocol planned double-blind visit is defined as the end of double-blind treatment period visit (Week 12).

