- All measurements, scheduled or unscheduled, fasting or not fasting, will be assigned to analysis windows defined in [Section 2.5.4, Table 2](#) in order to provide an assessment for Week 4 to Week 64 time points.
- In both the DBTP and the OLTP, for quantitative safety parameters based on central laboratory/reading measurements, descriptive statistics will be used to summarize results and change from baseline values by visit and treatment group using analysis windows. Summaries will also include the last on-treatment value and the worst on-treatment value. The last on-treatment value is defined as the last value collected during the treatment period of each observation period (see [Section 2.1.4](#)). The worst on-treatment value is defined as the nadir and /or the peak value during the treatment period of each observation period according to the direction (minimum or maximum) of the abnormality as defined in PCSA list.

Analyses performed according to diabetes status will be done using the CMQ definition (regardless of the ongoing status) ([Section 2.1.1](#)).

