For a conservative approach, the post-baseline status “Positive Ab – no RNA available” will not be modified by the availability of a second antibody test from a different assay.

For the description of the positive hepatitis C virus test during the TEAE period, all above rules applied by replacing post-baseline by TEAE period.

Drug-induced liver injury

The liver function tests, namely AST, ALT, ALP, and total bilirubin, are used to assess possible drug-induced liver toxicity. The proportion of patients with PCSA values or ALT increase as

defined in AESI section (see [Section 2.1.4.1](#)) during TEAE period by baseline status will be displayed by treatment group for each parameter.

An evaluation of drug-induced serious hepatotoxicity (eDISH) with the graph of distribution of peak values of ALT versus peak values of total bilirubin will also be presented using post-baseline values during TEAE period. Note that the ALT and total bilirubin values are presented on a logarithmic scale. The graph will be divided into 4 quadrants with a vertical line corresponding to 3 x ULN for ALT and a horizontal line corresponding to 2 x ULN for total bilirubin.

Listing of possible Hy's law cases identified by treatment group (ie, patients with any elevated ALT >3 x ULN, and associated with an increase in bilirubin >2 x ULN, concomitantly or not) with ALT, AST, ALP, total bilirubin, and if available, direct and indirect bilirubin will be provided.

The incidence of liver-related TEAEs will be summarized by treatment group. The selection of PTs will be based on SMQ Hepatic disorder (see [Section 2.4.5.1](#)).

Analysis of clinical laboratory variables in the open-label treatment period

For OLTP, summary tables as described for the DBTP above will be used with the following exception:

- Analyses by visit (unless data warrants further investigation)

Analysis of clinical laboratory variables in the alirocumab exposed period (first step analysis only)

For alirocumab exposed period, summary tables as described for the DBTP above will be used with the following exception:

- Analyses by visit (unless data warrants further investigation)

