2.4.5.4 Analyses of vital sign variables

The summary statistics (including number, mean, median, Q1, Q3, SD, minimum and maximum) of all vital signs variables (central laboratory values and changes from baseline) will be calculated for each visit or study assessment (baseline, each post-baseline value of the treatment period, last on-treatment, worst on-treatment value and follow-up visit) by treatment group. In addition for some parameters of interest; mean changes from baseline with the corresponding SE could be plotted over time (at same time points) in each treatment group.

Vital signs without position filled in will only be used for the PCSA analysis described below.

The incidence of PCSAs at any time during the TEAE period will be summarized by treatment group.

Analysis of vital signs variables in the open-label treatment period

For OLTP, summary tables as described for the DBTP above will be used with the following exception:

- Analysis by visit (unless data warrants further investigation)

Analysis of vital signs variables in the alirocumab exposed period (first step analysis only)

For alirocumab exposed period, summary tables as described for the DBTP above will be used with the following exception:

- Analyses by visit (unless data warrants further investigation)

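### The open-label on-treatment window (last dose + 21 days) is shorter than the Q4W interval, so on-schedule Q4W patients lose Week 64 from the last and worst on-treatment summaries while on-schedule Q2W patients keep it

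*SAP*

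**What the plan says.** SAP 2.1.4 defines the open-label TREATMENT period as running from the first open-label injection "up to the day of last dose of open-label IMP injection + 21 days". What follows is residual: "The open-label RESIDUAL TREATMENT period: defined as the time from the day of last dose of open-label IMP injection +22 days", up to + 70 days. There is one rule for both regimens.

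For the double-blind period the same section also uses + 21 days. It notes that for most Q4W patients this reaches about 35 days after the last active injection, because the Week 10 injection is placebo, and adds: "35 days is considered appropriate since the effect of alirocumab 150 mg Q4W is expected to be maintained during the 4-week dosing interval". No corresponding reason is given for the open-label period, which has no alternating placebo.

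Protocol 8.1.2 fixes the last doses: "In patients with alirocumab 150 mg Q4W, the last injection will be conducted at Week 60", and Week 62 for up-titrated Q2W. The end-of-OLTP visit is Week 64, Day 449 ± 5 (Protocol 10.1.4.10).

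SAP 2.4.5 says: "The last on-treatment value is defined as the last value collected during the treatment period of each observation period", referring back to 2.1.4. The worst on-treatment value is bounded in the same way. The same section plans, for both DBTP and OLTP, summaries of results and "change from baseline values by visit and treatment group using analysis windows". SAP 2.4.5.3 then reuses the DBTP laboratory tables for the OLTP with one exception, "Analyses by visit (unless data warrants further investigation"), and SAP 2.4.5.4 makes the same exception for vital signs.

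**The concern.** A 21-day tail closes 7 days before the next Q4W dose would fall due (28 − 21). It closes 7 days after the next Q2W dose would fall due (21 − 14). Week 64 is the end of the final Q4W dosing interval, yet the rule classes it as residual for Q4W patients dosed on schedule.

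Long-term open-label safety on both regimens is a secondary objective, and SAP 2.4.5 presents the OLTP for all patients together. The last-value tables would then mix Week 48 values from Q4W patients with Week 64 values from Q2W patients. The Q2W patients are also a selected group, up-titrated because their Week 20 LDL-C was above threshold. If the exceptions in 2.4.5.3 and 2.4.5.4 govern, no other routine quantitative open-label table shows the Week 64 laboratory and vital-sign values.

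**Working it through.** **Inputs.** Study day = 7 × week + 1, as in the flow chart (Protocol 1.2): Week 36 = Day 253, Week 48 = 337, Week 60 = 421 (± 7, so 414–428), Week 64 = 449 (± 5, so 444–454). Week 62 = 7 × 62 + 1 = Day 435. The protocol lists no visit window for Week 62, so ± 7 is assumed where one is needed.

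**The SAP's own figure.** Double-blind Q4W: last active dose Week 8 = Day 57, last (placebo) injection Week 10 = Day 71. Window end 71 + 21 = 92, and 92 − 57 = 35 days. The stated 35 days is reproduced, and it depends on the Week 10 placebo.

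**Same rule, open label, dosed on schedule.**

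| Regimen | Last dose | Window end | Week 64 days 444–454 inside |
|---|---|---|---|
| Q4W, + 21 | 421 | 442 | 0 of 11 |
| Q2W, + 21 | 435 | 456 | 11 of 11 |
| Q4W, + 28 | 421 | 449 | 6 of 11 |
| Q4W, + 35 | 421 | 456 | 11 of 11 |

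**Off-schedule dosing.** A Week 64 visit on Day v counts only if the last dose was on or after Day v − 21. The earliest visit needs a dose on Day 423 or later (444 − 21). The nominal visit needs Day 428 (449 − 21), the last day of the Week 60 window.

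There are 15 × 11 = 165 permitted pairs of dose day and visit day:

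- Q4W, + 21: 1 + 2 + 3 + 4 + 5 + 6 = 21 pairs inside (12.7%).
- Q4W, + 35: 165 − (5 + 4 + 3 + 2 + 1) = 150 pairs inside (90.9%).
- Q2W, + 21, with the assumed ± 7: also 150 of 165.

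This counts permitted days with equal weight and does not forecast where visits will fall.

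**What the last on-treatment value becomes.** With no later unscheduled sample, laboratory tests, heart rate and blood pressure fall back to Week 48, a gap of (449 − 337)/7 = 16 weeks. Body weight is not measured at Week 48 and falls back to Week 36, a gap of (449 − 253)/7 = 28 weeks.

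**Exposure (secondary).** SAP 2.4.3.1 adds 14 days to the last open-label dose. The first open-label dose is at Week 12, Day 85 (82–88).

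- Q4W completer, + 14: (421 + 14 − 85)/7 = 50.0 weeks. Range within visit windows: (414 + 14 − 88)/7 = 48.6 to (428 + 14 − 82)/7 = 51.4.
- Q4W completer, + 28: (421 + 28 − 85)/7 = 52.0 weeks, range 50.6 to 53.4.
- Q2W completer, + 14: (435 + 14 − 85)/7 = 52.0 weeks.

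The target of 100 patients with 12 months on alirocumab uses all three arms. With 36% dropout, 159 × 0.64 = 101.8, but the two alirocumab arms alone give 106 × 0.64 = 67.8. The rest are former placebo patients, whose only alirocumab exposure is open-label.

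**The case against.** The strongest reply concerns consequence, since the day arithmetic is not in dispute. Open-label safety is descriptive, with no comparator and no testing. The outputs that detect abnormal values (PCSA incidence, ALT and Hy's law listings, eDISH) use the TEAE period of last dose + 70 days and keep Week 64 for everyone. This stands, and it limits the problem to the last and worst rows of the second-step tables.

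If the general rule in 2.4.5 governs, Week 64 appears by visit and less is lost. That is fair, but the specific exceptions in 2.4.5.3 and 2.4.5.4 say otherwise, and the last and worst values are wrong under either reading.

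The pair count can also be challenged. All 21 included pairs come from late Week 60 doses, and delays of up to 7 days are allowed. Counting only on-time or late doses gives 21 of 88 (23.9%). The picture changes in degree only, because most Week 64 visits are still lost.

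On exposure, patients randomised to alirocumab have the double-blind weeks as well, and every Q4W completer dosed within the visit windows stays in the top open-label category (48 weeks or more). Both points are right. The effect is on the continuous summary and on former placebo patients.

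Finally, + 35 would count values up to a week after the next due dose for Q4W patients who stop early. That is the same 7-day margin that + 21 already gives Q2W patients.

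**Conclusion.** The concern holds. For Q4W patients dosed on schedule, the open-label window excludes every permitted Week 64 visit day, while for Q2W patients dosed on schedule it includes every one. The SAP's reason for its double-blind window does not carry over to open-label Q4W. The last scheduled on-treatment value falls 16 weeks short of Week 64 for laboratory tests, heart rate and blood pressure, and 28 weeks short for body weight. Worst on-treatment values omit Week 64 as well.

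This rests on dosing on schedule and on no later unscheduled sample. The documents do not say how many patients will still be on Q4W at Week 60, so the extent of mixing in the pooled tables is unknown.

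TEAE, PCSA, eDISH, ECG, on-treatment death, HbA1c by-visit and antibody outputs are unaffected, as is the first-step (Week 24) analysis. The effect on the open-label count of patients with two consecutive LDL-C values below 25 mg/dL depends on whether the treatment period in SAP 2.1.5 means the defined TREATMENT period or the whole OLTP. The plan should be corrected before the final analysis, but no efficacy conclusion is at risk.

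**What to change.** - In SAP 2.1.4, for patients on Q4W at their last open-label dose, end the open-label TREATMENT period at + 35 days and start the RESIDUAL period at + 36. Keep + 21 and + 22 for patients on Q2W. On-schedule patients on either regimen then share the same end day (456).
- Reconcile 2.4.5 with 2.4.5.3 and 2.4.5.4 by stating whether open-label laboratory and vital-sign results are summarised by visit.
- In 2.1.5, state which treatment period bounds the LDL-C below 25 mg/dL count.
- In 2.4.3.1, compute open-label exposure as last dose + 28 days for patients on Q4W at last dose, and + 14 for Q2W, so that a completed 52-week OLTP is reported as 52 weeks on either regimen.

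The cost is SAP wording and a regimen-dependent derivation from data already collected. Dosing and visits do not change. The one drawback is having two conventions in place of one.
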